## STUDY SYNOPSIS

|                                      |  |
|--------------------------------------|--|
| Sponsor-Investigator          | Dre [name]
Pharmacist
Centre de Pharmacie Communautaire,
Policlinique Médicale Universitaire,
[name]   |
| Study Title:                  | Randomised, Controlled Trial of an Individual Deprescribing Intervention for Nursing Homes' Residents.   |
| Short Title/Study ID:         | OLD-NH-IDel study  |
| Protocol Version and Date:    | Protocol version 2 of 27.08.2018   |
| Trial registration:           | The study will be registered with ClinicalTrials.org; no registration number available at the time of submission. In addition, this study will be registered with the Swiss National Clinical Trial Portal (KOFAM).  |
| Study category and Rationale  | As the study involves minimum risk for the participant and will be conducted under the constant supervision of health professionals, this study is deemed of risk category A.  |
| Clinical Phase:               | Not applicable to this study   |
| Background and Rationale:     | Older people residing in nursing homes (NH) are frequently polymedicated and often prescribed potentially inappropriate medications (PIMs). Deprescribing has been proposed as a way to reduce the number of drugs they receive and their exposure to harmful treatments.

In the nursing homes of Vaud and Fribourg, physicians, nurses and pharmacists are already working together in quality circles to improve drugs use. This provides an excellent opportunity to implement a deprescribing intervention, using the collaboration already in place. |
| Objectives:                   | The primary study objective is to determine the effect of a pharmacist-led, deprescribing-focused medication review on the use of PIMs by NH residents.

The main secondary objectives are to determine the safety of this intervention and its effect on the participants' quality of life.   |
| Outcomes:                     | The primary outcome is the change in the number of PIMs used by participants between baseline and 4 months (end of follow-up).

The main secondary outcomes are the mortality rate, hospitalisation rate, number of falls and quality of life measured with EQ-5D-5L. This intervention will also be evaluated on implementation outcomes.   |

| Investigators:                         | [name]
Centre de Pharmacie Communautaire,
Policlinique Médicale Universitaire,
[name]
[contact]
[contact] (secretary)

[name]
Centre de Pharmacie Communautaire,
Policlinique Médicale Universitaire,
[name]
[contact]
[contact]                            |
| Study Centre:                          | This study is monocentric; however, the intervention will take place in different NHs of the Cantons of Vaud and Fribourg.   |
| Statistical Considerations:            | Generalised linear mixed models will be used for the analysis of outcomes relative to individual participants; outcomes at the NH level will be analysed using t-tests or Mann-Whitney, according to distribution.   |
| GCP Statement:                         | This study will be conducted in compliance with the protocol, the current version of the Declaration of Helsinki, the ICH-GCP as well as all national legal and regulatory requirements.   |

## ABBREVIATIONS

|        |   |
|--------|---|
| AE     | Adverse Event   |
| BASEC  | Business Administration System for Ethical Committees,                                |
| CA     | Competent Authority   |
| CEC    | Competent Ethics Committee  |
| CER-VD | Commission cantonale d'éthique de la recherche sur l'être humain
du Canton de Vaud |
| CRF    | Case Report Form  |
| ClinO  | Ordinance on Clinical Trials in Human Research  |
| eCRF   | Electronic Case Report Form   |
| CTCAE  | Common terminology criteria for adverse events  |
| DDD    | Defined Daily Dose  |
| GCP    | Good Clinical Practice  |
| Ho     | Null hypothesis   |
| H1     | Alternative hypothesis  |
| HRA    | Federal Act on Research involving Human Beings  |
| IIT    | Investigator-initiated Trial  |
| ITT    | Intention to treat  |
| NH     | Nursing Home  |
| PI     | Principal Investigator  |
| PIM    | Potentially Inappropriate Medication  |
| RCT    | Randomised, Controlled Trial  |
| SUSAR  | Suspected Unexpected Serious Adverse Reaction   |

### 1.4 Laboratory

No laboratory will be involved in this study.

## **1.6 Data Safety Monitoring Committee**

As defined in ICH's GCP guidelines, section 1.25 [1], the role of the data safety monitoring committee is “*to assess at intervals the progress of a clinical trial, the safety data, and the critical efficacy endpoints, and to recommend to the sponsor whether to continue, modify, or stop a trial.*”

The anticipated duration of the trial as a whole (9 months) and for individual participants (4 months) are short and extremely close: most participants will enter the study at the same time, and no intermediate data collection and analysis are planned. Thus, all participants will have entered the study before any individual participant completes it. As no intermediate data collection and analysis are planned, a data safety monitoring committee would not have the opportunity to review data and inform the sponsor on whether to continue, modify, or stop the trial. For this reason, no data safety monitoring committee will be constituted.

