## **2.9 Early termination of the study**

The Sponsor-Investigator may terminate the study prematurely if the NHs where the study takes place express concerns regarding the safety of the participants. The CER-VD will be informed within 15 days in case of premature termination.

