After randomisation, the record of participants allocated to the intervention group will be searched by the nurse responsible for the study in the NH ("study nurse") for clearly stated objectives of care. If no objectives are present in the record, the referent nurse for this participant will be interviewed by the pharmacist to clarify these objectives. The referent nurse will also provide a list of drugs taken by the participant without supervision of the NH staff (self-medication). Using this information and the content of the participant's records in the NH and in the pharmacy, the pharmacist will then conduct the medication review according to the formation received; the medication review process is described in chapter 8, page 20. Based on the results of the medication review, a deprescribing plan will be decided by the NH care team (head nurse, physician(s) responsible for the resident(s), and pharmacist). This plan will also include proposition for the introduction of new drugs if prescription omissions (sub-optimal treatment) are detected by the medication review. Each item of this plan will then be presented for validation to the participant or her/his representative. Once validated, baseline data collection will occur and the deprescribing plan will be implemented.

Participants allocated to the control group will receive usual care. Baseline data collection for them will occur after inclusion. Follow up data collection will occur 4 months after baseline data collection for both groups. The duration of the study will be 4 months for the participants allocated to the control group. For participants allocated to the intervention group, the realisation of the medication review by the pharmacist, the discussion of its results with the treating physicians, the creation of the deprescribing plan, and its discussion with the participant will induce a delay before baseline data collection, estimated of maximum 2 months; thus, the total duration of the study could be up to 6 months in this group. Participants allocated to both groups will be monitored as usual by the NH care team (treating physician and nurses) during and after the duration of the study. In addition, the NH care team will mention specific monitoring measures in the deprescribing plan, according to the drugs being deprescribed and the clinical situation of the participant.

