### 9.2.5 Assessments in participants who prematurely stop the study

In case of participant death before completion of follow-up, the follow-up CRF (staged for completion at visit 2) will be completed within 7 days by the pharmacist and nurse. For the assessment of the treatment plan regarding PIM status, the pharmacist will take into account the treatment plan of the day preceding death. No information will be collected regarding quality of life and common complaints.

If a participant is hospitalised at the date of the follow-up visit, the same procedure as for the participant having died is applied. The treatment plan of the day preceding the hospitalisation will be taken into account.

If a participant wishes to stop the study before the follow-up visit, she/ he will be offered to complete the quality of life and common complaints questionnaire before exiting the study.

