## **10.2 Reporting of serious adverse events (SAE) and other safety related events**

### **10.2.1 Reporting of SAEs**

All SAEs will be reported to the investigators within a week of occurrence by the study nurse, using a specific CRF (see Annex 16). The investigators will contact the NH care team to discuss in details the situation. If necessary, the advice of a geriatrician ([name], CHUV) will be solicited by the investigators for the discussion of the SAE with the NH care team. For the cases where a causal link with the intervention remains probable or definitive after investigation, the CER-VD will be informed within 24 hours via BASEC. In all cases, reported SAEs will be reported to the CER within 15 days via BASEC.

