### **10.2.5 Periodic reporting of safety**

As the duration of this study is less than a year, no interim safety reports will be submitted. Safety will be assessed in the final report to the EC.

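### Section 1.6 says a safety committee would have no data to review, yet SAEs and deaths reach the study centre within about a week, and no cumulative by-arm review across homes is planned

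*Combined protocol and SAP*

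**What the plan says.** Section 1.6 gives two reasons for having no committee. The first is lack of data: "As no intermediate data collection and analysis are planned, a data safety monitoring committee would not have the opportunity to review data". The second is timing: with 9 months for the trial and 4 for a participant, "all participants will have entered the study before any individual participant completes it".

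Other sections bear on these reasons:

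- Section 10.2.1: "All SAEs will be reported to the investigators within a week of occurrence by the study nurse". It adds: "In all cases, reported SAEs will be reported to the CER within 15 days via BASEC". The limit is 24 hours where a causal link remains probable or definitive.
- Section 9.2.5, on a death before the end of follow-up, without restriction to one arm: "the follow-up CRF (staged for completion at visit 2) will be completed within 7 days by the pharmacist and nurse".
- Section 6.1, on the intervention group, whose baseline may come up to 2 months after inclusion: "thus, the total duration of the study could be up to 6 months in this group".
- Section 2.9: "The Sponsor-Investigator may terminate the study prematurely if the NHs where the study takes place express concerns regarding the safety of the participants". Section 11.3 sets no discontinuation criteria.
- Section 10.2.5, having ruled out interim safety reports: "Safety will be assessed in the final report to the EC". Section 2.3 puts that report within one year of completion.
- Section 12.2.2 limits each home's REDCap access to its own residents. Section 12.3 has an independent monitor following all homes weekly through REDCap.

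**The concern.** The reason given for having no committee does not match the plan's own reporting rules. The most serious safety data reach the study centre while the trial is running, and the plan asks nobody to look at them together.

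This matters because deaths are expected in this population, so a moderate excess would look like background when cases are discussed singly with the home concerned. Section 3.8 expects many participants to be cognitively impaired. The homes, whose concern is the one termination ground named, each see too few residents to recognise an excess.

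**Working it through.** **1. Residents per home.** Section 11.2 gives half of 18 homes, a mean of 59 beds and 20% recruited: 9 × 59 × 0.20 = 106.2, which reproduces the stated 106. With 1:1 allocation within home (6.2.1), intervention residents per home are 59 × 0.20 / 2 = 5.9, or about 53 in the trial. Section 6.1 uses 10 homes of 50 residents: 50 × 0.20 / 2 = 5.0 per home, or 50 in the trial. Hence 5 to 6 per home.

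**2. What arrives during the trial.**

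| Data | When | Arms |
|---|---|---|
| SAEs (10.2.1) | within a week | mainly intervention, because 10.1 counts an AE only if a link with the intervention cannot be excluded |
| Deaths (9.2.5) | form within 7 days | both |
| Falls, restraint days, other hospital stays (9.2.4, 9.3.2) | normally visit 2 | both |

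The no-data premise therefore fails for SAEs and deaths. It holds for most other safety outcomes.

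**3. Timing.** If a participant can need 6 of the 9 months, inclusion can run for up to 9 − 6 = 3 months. A control included in month 0 finishes in month 4. An intervention resident included in month 3 may reach implementation only in month 3 + 2 = 5. Everyone has still entered before anyone completes, so that statement survives. It limits what a review could do about enrolment, but the trial could still be modified or stopped.

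**4. What a home and a pooled review could see.** The documents give no death rate. As an assumption, take the mean stay of under 3 years (3.4) as exponential with mean 36 months, every stay ending in death:

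- Four-month risk: 1 − exp(−4/36) = 10.5%. With the hazard doubled: 1 − exp(−8/36) = 19.9%.
- One home, n = 6: 0.6 v 1.2 deaths expected; P(3 or more) = 2% v 10%.
- Pooled intervention arm, n = 53: 5.6 v 10.6 deaths expected; P(10 or more) = 5% v 63%.

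The 63% treats the control rate as known and counts deaths after all 53 have had 4 months of follow-up. With 2 months of exposure the risks are 1 − exp(−2/36) = 5.4% and 1 − exp(−4/36) = 10.5%, and P(10 or more) under the doubled hazard is 5%.

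The comparison a by-arm table supports is 53 v 53. With Fisher's exact test, two-sided 5%, power is about 0.19 at 4 months and 0.07 at 2 months.

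**5. Range.** For assumed four-month control risks of 5% to 20%, with the risk doubled in the intervention arm:

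- An exact one-arm flag with a false-alarm rate of at most 5% fires with probability 0.11 to 0.26 in one home and 0.44 to 0.91 pooled.
- An approximate two-arm test on 53 v 53 has power 0.16 to 0.62.

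Pooling helps at every rate tried, but it does not make the review decisive.

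**The case against.** The strongest reply is that trial-level oversight already exists. Unblinded investigators receive every SAE, assess causality (10.1.1) and check progress weekly (8.4). The ethics committee receives every reported SAE within 15 days and has constant access to all documents and data (12.4), and section 2 commits the sponsor to any requirement the authorities impose. Treating physicians stay in control throughout (7.4), and the study is category A. This stands. A reader might infer that nobody outside the homes looks at safety before the final report; the documents do not support that. They do support the narrower statement that nobody is asked to count events by arm across homes.

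Secondly, 2.9 says when the sponsor-investigator may terminate and does not say only then. That is right: a reader might infer that no other ground is allowed, but the text does no more than name no other.

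Thirdly, the 6-month duration might be taken to refute the timing argument. It does not, as step 3 shows. Six months is also closer to 9 than 4 is.

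Fourthly, nine homes are watching, not one. At 10.5% risk doubled to 21%, the chance that at least one home of nine sees 3 or more intervention deaths is 0.66, but it is already 0.15 with no excess. The pooled rule of 10 or more gives 0.70 at a false-alarm rate of 0.05.

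Finally, an SAE table by arm would mislead. Under 10.1 control-arm SAEs will be few by definition, so an excess would appear even without harm. This is correct and shapes the fix.

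**Conclusion.** The point holds in a limited form. The no-data rationale in 1.6 is wrong for SAEs and deaths, and its 4-month individual duration conflicts with the 6 months allowed in 6.1. No section plans a cumulative review by arm across homes, and the one termination ground named depends on homes with about 5 to 6 intervention residents each.

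The case rests on these mismatches and not on the mortality illustration, whose rates are assumed. It would be tempting to say that pooled review would probably catch a doubling of mortality, citing the 63%. That figure needs a known control rate and complete follow-up. The two-arm figures of 0.19 and 0.07 are the fair guide, and even they assume that the doubled hazard applies throughout the exposure counted. Time before implementation would dilute the contrast further. The change is worth making because it costs little and protects a vulnerable population. The documents do not show that a formal committee is needed.

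**What to change.** 1. In 1.6, state that SAEs and deaths are reported during the trial and that individual duration is up to 6 months in the intervention group. Rest the decision against a committee on grounds that remain true, such as the short trial and nearly simultaneous entry.
2. Have the independent monitor of 12.3 tabulate deaths by allocation across all homes at stated intervals (monthly would be workable). Count deaths and time at risk from randomisation in both arms, because baseline is delayed by up to 2 months in one arm only. Since 5.4 counts mortality from baseline, confirm that a death between randomisation and visit 1 also triggers the form in 9.2.5.
3. List SAEs cumulatively for the intervention arm, without a between-arm comparison.
4. Send both to the sponsor-investigator and the geriatrician already mentioned in 10.2.1.
5. Extend 2.9 so that the study may be suspended or terminated on this cumulative review as well as on concern from the homes.

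**Cost.** A few sentences and one recurring REDCap table, with no new staff and essentially no new data. The investigators would see accumulating safety counts by arm, but 6.2.2 already leaves them unblinded. The efficacy outcome is not examined, so the type I error of the primary analysis is unaffected. The text should say that the review is a safeguard with low power, so that a quiet table is not read as evidence of safety.

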## **1.7 Other relevant Committee, Person, Organisation or Institutions**

No other committee, person, organisation or institution other than the participating NHs will take part in this study.

## **2. ETHICAL AND REGULATORY ASPECTS**

The decision of the CEC concerning the conduct of the study will be made in writing to the Sponsor-Investigator before commencement of this study. The recruitment of participants will begin once approval from all required authorities has been received. Any additional requirements imposed by the authorities shall be implemented.

### **2.1 Study registration**

This study will be registered with the ClinicalTrials.gov registry; registration is ongoing and no registration number is available at the time of submission. Registration will be completed before inclusion of the first patients.

In addition, this study will be registered with the Swiss National Clinical Trial Portal.

### **2.2 Categorisation of study**

As this trial is not one of a drug, medical device, or transplant, it is classified as an “Other Clinical Trial”, according to ClinO article 60.

Since all treatments alterations conducted must be judged as safe by the treating physician caring for each participant (see section 8.1.1, page 20) and will be conducted in a setting with constant monitoring, the risks are judged minimal by the investigators. The data collection methods involve no blood or tissue sampling, nor the collection of broad health-related data; the burden of the trial is thus deemed minimal. For these reasons, this study is of category A, according to ClinO article 61.1.

### **2.3 Competent Ethics Committee (CEC)**

As this project will take place in the cantons of Vaud and Fribourg, the Commission cantonale d'éthique de la recherche sur l'être humain of Canton de Vaud (CER-VD) is competent. Investigators will submit the present study protocol to the CER-VD for approval. No patient will be recruited before reception of the written agreement of the CER-VD.

The end of the study will be reported to the CER-VD within 90 days of completion (last collection of data); the study report will be submitted within one year of completion. In case of premature study end or study interruption, the CER-VD will be informed within 15 days.

### **2.4 Competent Authorities**

No approvals from other competent authorities are necessary for this research project, as it is of risk category A.

### **2.5 Ethical Conduct of the Study**

The study will be carried out in accordance to the protocol and with principles enunciated in the current version of the Declaration of Helsinki [2], the guidelines of Good Clinical Practice (GCP) issued by ICH [1], as well as the Swiss Law and Swiss regulatory authority's requirements. The CER-VD will be informed about

study end, in agreement with the Swiss law; given the duration of the study, no interim reports are planned.

## **2.6 Declaration of interest**

The sponsor, investigators and statistician declare no conflicts of interest, be they intellectual, financial or of any other kind.

## **2.7 Patient Information and Informed Consent**

Each participant, or her/his legal representative if applicable, will be informed of the nature of the study, its purpose, the procedures involved, the expected duration, the potential risks and benefits and any discomfort it may entail. Each participant or his/her representative will be informed that the participation in the study is voluntary, that he/she may withdraw from the study at any time, and that withdrawal of consent will not affect his/her subsequent medical assistance and treatment.

The participant will be informed that his/her medical records may be examined by authorised individuals other than their treating physician.

All participants for the study will be provided a participant information and consent form (see Annex 1) describing the study and providing sufficient information for participant to make an informed decision about their participation in the study. For participants unable to consent because of cognitive impairment, the consent of their legal representatives will be necessary (see Annex 2). Participants or their representative will be given at least 24 hours to review the documents before deciding to enrol or not in the study.

The formal consent of a participant, or of her/his representative, using the approved consent form, will be obtained before the participant is submitted to any study procedure.

The participant or her/his representative, after being given enough time to read and consider the statement, will read and date the informed consent form, and will be given a copy of the signed document. The consent form will also be signed and dated by the investigator's representative at the same time as the participant sign, and it will be retained as part of the study records.

